
Test Product, Dose and Mode of Administration:
 
Racecadotril Infants Granules for Oral Suspension 10 mg Racecadotril Children Granules for Oral Suspension 30 mg
 
1.5 mg/kg of Racecadotril will be administered, 3 times daily, via the oral route.
 
In infants less than 9 kg: one 10 mg sachet 3 times daily. In infants from 9 kg to < 13 kg: two 10 mg sachets 3 times daily. In children from 13 kg to 27 kg: one 30 mg sachet 3 times daily. In children of more than 27 kg: two 30 mg sachets 3 times daily.
 
Racecadotril will be given three times daily in addition to standard treatment ORS. For concomitant medication (please see section 7.7).
 
Standard treatment is oral rehydration solution (ORS) according to the registered local label and the instruction of the investigator. At the start of the trial, alignment will be reached on the understanding of treatment of standard ORS with the principal investigator with the aim to use the same brand of ORS and the same age-appropriate standardized treatment pattern for the subjects throughout the trial.
		

Duration of Treatment:
 
The first dose of Racecadotril will be taken on day 1, either noon, or evening dose. The treatment duration lasts until recovery (last dose in the morning after recovery), maximally 5 days, until the morning dose of day 6.
		

Criteria for Evaluation:
 
Efficacy:
 
Primary Efficacy Variable: Duration of diarrhea (hours) between the start of treatment until last diarrheal/watery stool before recovery or end of study treatment (treatment duration maximal 5 days). Duration of diarrhea is defined as date and time of the evacuation of the final watery/diarrheal stool before recovery
		

Name of Sponsor: Abbott Taiwan	Name of Finished Product: Hidrased Infants Granules for Oral Suspension 10 mg Hidrased Children Granules for Oral Suspension 30 mg	Name of Active Ingredient(s): Racecadotril

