Subjects will be treated with Racecadotril three times daily according to the body weight dose requirement on an out-patient basis for maximum 5 days. The subjects will be treated with ORS (according to the registered local label and the instruction of the investigator) in addition to Racecadotril. ORS will be prescribed by the investigator and will be taken according to the product label and the instruction of the investigator. The parent(s)/caregiver(s)/legal representative(s) will be instructed to stop study drug treatment when the patient recovered. On each day, the parent(s)/caregiver(s)/legal representative(s) will fill in their diaries, documenting the date and time of each individual stool, the stool consistency of each stool (diarrheal/watery or normal), the amount of ORS, and the study drug intake. After the occurrence of two consecutive normal stools or no stool within 12 hours, the parent(s)/caregiver(s)/legal representative(s) can stop recording of the diary and return to the study site for the end of treatment visit. The date of recovery is the day when the first of two consecutive normal stools were excreted or the day

[figure not shown]
when no stool within 12 hours after the first normal stool was observed. AEs are to be reported on an ongoing basis.

End of treatment (Day 6 or early recovery, Visit 2)

The last dose of study drug will be the morning dose of day 6, if not recovered earlier (last dose will be the morning dose after recovery, ORS can be continued until Visit 2). On the same day, or within 24 hours after recovery (in exceptional cases within 48 hours), the parent(s)/caregiver(s)/legal representative(s) will visit the site for the end of treatment visit of the child. Data on vital signs, AEs, physical examination and concomitant medication will be collected. Subjects will return their diaries and unused medication.

Safety follow-up

A phone call will be performed 5-7 days after the end of the treatment period for the safety follow-up.

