8.3 Other Assessments

Informed Consent

Voluntary written informed consent must be obtained from one parent/legal representative prior to performing any study-related procedures (see Section 1.3).

Demographic Data

Demographic data (gender, age, year and month of birth, race) will be collected for all subjects.

Medical History

Any clinical event, including diagnosis, condition, or surgery, that occurred prior to allocation to treatment, is to be recorded on the Medical History form. In case a clinical event concerns a chronic disorder, which means it started in the past and it is still present at the screening visit, it should also be recorded on the Medical History Form. Examples of these events are diabetes, migraine, and hay fever.

Concomitant Medication

All medication taken by the subject during the study (from signing the informed consent form through post-study follow-up) is to be recorded on the Concomitant Medication form, except for study drug.

Subject Diary

The parent(s)/caregiver(s)/legal representative(s) have to document date and time of each individual stool of the subject and the stool consistency (watery, normal) of each evacuation continuously. The subject individual stool consistency before start of the diarrhea is defined as normal (e.g. taking into account the age and diet, e.g. breast feeding, of the individual subject).

Recording can be stopped after the excretion of two consecutive normal stools or no stool within 12 hours.

The date, time and dose of study drug intake as well as the amount ORS consumed has to be recorded.

Fever will be measured twice daily, once in the morning and once in the evening with at least 12-hour interval using the same device and method (preferably ear temperature), by the parent(s)/caregiver(s)/legal representative(s) and documented in the diary including method, time and value.

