10.1 Extent of Exposure

The way of computing the extent of exposure is listed as below,

The extent of exposure = The date of completion/ termination of the study treatment drug intake - The date of the first study treatment drug intake) + 1]

Number of sachets scheduled to be taken during that treatment period is the collected data from diary card before the last dose (last dose was defined the first dose of the next day after recovery). The extent of exposure for the treatment group will be summarized as Table 14.1.3 using Safety, FA and PP Samples.

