10.2 Drug Compliance

The way of computing the drug compliance is listed as below,

The study drug compliance = Number of sachets a subject takes during the treatment period / Number of sachets scheduled to be taken during that treatment period)*100%

The drug compliance for the treatment group will be summarized as Table 14.1.3 using Safety, FA and PP samples as well.

11.SAFETY ANALYSIS

The safety sample will be used for the analysis of the safety and tolerability data.

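### SAP 10.1 leaves the last required dose out of scheduled sachets and SAP 10.2 states no matching cut-off, so compliance either exceeds 100% at full adherence or cannot show a skipped last dose

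*SAP*

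**What the plan says.** The synopsis (Duration of Treatment) places the dose after recovery inside treatment: "The treatment duration lasts until recovery (last dose in the morning after recovery), maximally 5 days, until the morning dose of day 6". Protocol 4.1 repeats this: "last dose will be the morning dose after recovery, ORS can be continued until Visit 2". For a child who has not recovered, 4.1 says: "The last dose of study drug will be the morning dose of day 6, if not recovered earlier".

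SAP 10.1 uses the same last dose ("last dose was defined the first dose of the next day after recovery") but stops the denominator short of it: "Number of sachets scheduled to be taken during that treatment period is the collected data from diary card before the last dose". The numerator in SAP 10.2 is "Number of sachets a subject takes during the treatment period", with no cut-off before the last dose. The exposure formula in SAP 10.1 runs through the date on which drug intake ends, so the day of the last dose counts as exposure although its dose is not scheduled. Exposure and compliance both go into Table 14.1.3 for the Safety, FA and PP samples.

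On the data source, protocol 8.3 says of the diary: "The date, time and dose of study drug intake as well as the amount ORS consumed has to be recorded". It also says: "Recording can be stopped after the excretion of two consecutive normal stools or no stool within 12 hours". Protocol 7.8 expects every intake to be entered in the diary, and requires used and unused supplies to be inventoried and returned.

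**The concern.** A compliance percentage should be doses taken over doses required. Here the denominator omits a required dose, and the numerator, as worded, need not. Depending on how the programmer resolves this, perfect adherence scores above 100%, or the last dose drops out of the measure. Neither gives the intended quantity.

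The rule applies to every child who recovers. The sample-size text (protocol 10.8, SAP 4.4) plans on at least 99% recovering after 3 days of treatment, so nearly every child would be affected. The distortion is largest for early recovery, because one dose is then a bigger share of the total. What is at stake is the meaning of the compliance summary that protocol 10.5 calls for.

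**Working it through.** The documents give no compliance figure to reproduce, so the check counts doses under the stated rules.

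**Inputs**
- Three dosing slots a day: morning, noon, evening (protocol 7.1).
- First dose at noon or evening of Day 1 (protocol 4.1), so Day 1 has 2 doses or 1.
- Recovery on Day d; last dose on the morning of Day d+1 (synopsis; SAP 10.1).
- One or two sachets per dose by weight (protocol 7.1). With a constant number the ratio is unchanged: for 9 doses, 18/16 = 9/8 = 112.5%.
- Assumption: all slots through the evening of the recovery day are due.

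**Formulas**
- Doses before the last dose: b = 2 + 3(d-1) for a noon start, 1 + 3(d-1) for an evening start.
- Required doses: n = b + 1.
- Reading A (numerator covers the whole treatment period, last dose recorded): full adherence scores n/b = n/(n-1).
- Reading B (numerator cut where the denominator is cut): b/b = 100%, last dose taken or not.
- Doses taken over doses required: n/n = 100% at full adherence; (n-1)/n if only the last dose is skipped.

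| Start | Recovery day | b | n | Reading A, full adherence | Correct score, last dose skipped | Excess under reading B (points) |
|---|---|---|---|---|---|---|
| Noon | 2 | 5 | 6 | 120.0% | 83.3% | 16.7 |
| Noon | 3 | 8 | 9 | 112.5% | 88.9% | 11.1 |
| Noon | 4 | 11 | 12 | 109.1% | 91.7% | 8.3 |
| Noon | 5 | 14 | 15 | 107.1% | 93.3% | 6.7 |
| Evening | 2 | 4 | 5 | 125.0% | 80.0% | 20.0 |
| Evening | 3 | 7 | 8 | 114.3% | 87.5% | 12.5 |
| Evening | 4 | 10 | 11 | 110.0% | 90.9% | 9.1 |
| Evening | 5 | 13 | 14 | 107.7% | 92.9% | 7.1 |

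Recovery on Day 1 would give 3/2 = 150% or 2/1 = 200% under reading A.

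**Larger non-adherence.** Under reading A it still shows, but understated. Noon start, recovery on Day 3, last dose taken: one earlier dose missed gives 8/8 = 100% against a correct 8/9 = 88.9%; two missed give 7/8 = 87.5% against 7/9 = 77.8%.

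**Same doses, different scores.** After a noon start, a child treated through the Day 6 morning dose takes 2 + 4×3 + 1 = 15 doses. Recovered on Day 5, reading A gives 15/14 = 107.1%. Not recovered, with all slots counted, 15/15 = 100%.

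**Sensitivity to the assumption.** If doses on the recovery day after recovery are not due, n falls and n/(n-1) rises. Noon start, recovery on Day 3: without the evening dose 8/7 = 114.3%; without noon and evening 7/6 = 116.7%, against 112.5% in the table.

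**The case against.** The best reply is that SAP 10.2 refers both counts to one treatment period, which points to a single window and so to reading B. That stands in part. A reader might infer that scores above 100% are certain to appear; the text does not support this, since it leaves both readings open.

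The reply continues that leaving the last dose out is sensible. Protocol 4.1 tells caregivers to stop study drug on recovery, and 8.1 says treatment stops then. Diary entries may end once recovery is confirmed. Visit 2, where unused drug is handed back, falls within 24 hours of recovery (48 in exceptional cases), and recovery is timed at the first normal stool. A child seen before the next morning no longer holds drug and should not be scored as having missed that dose. This stands, and the remedy has to allow for it. It does not rescue the present rule, because the synopsis and 4.1 qualify the instruction to stop by naming the next morning's dose as the last one, and the SAP adopts that definition.

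A reader might also infer three further faults that the documents do not support:
- That an unrecovered child has no end of treatment in the SAP. SAP 3.5 ends treatment after the Day 6 morning dose. What is missing is a link from the sachet count to that rule, and any rule for withdrawal.
- That taking the schedule from the diary hides all missed doses. The diary form is not among the documents, so this cannot be judged.
- That efficacy results or PP membership are affected. The PP definition states no compliance threshold, and no efficacy analysis uses compliance.

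**Conclusion.** The point holds as a wrong counting rule of limited reach. For recovered children the SAP as written gives either about 107 to 125% at full adherence (recovery on Days 2 to 5), or a score that cannot distinguish a taken last dose from a skipped one and is 6.7 to 20 points too high when it is skipped. The documents do not settle which will occur. Because diary recording may lawfully stop before the last dose, that dose may be recorded for some children and not for others, so the summary could mix the two.

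The percentages illustrate the rule and do not predict the table. They rest on all recovery-day doses being due, a constant number of sachets per dose and, for reading A, a recorded last dose. The error is one dose per recovered child in a descriptive summary, and Listing 16.2.5.2 with the returned-drug inventory allows individual checking. The correction is still worth making, because the summary would otherwise not report doses taken over doses required.

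**What to change.** In SAP 10.1, replace the scheduled-sachets sentence with:

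> Scheduled sachets = sachets per dose for the weight band × dosing slots from the first dose up to and including the first dose of the day after recovery, or the Day 6 morning dose if not recovered, or the last slot before withdrawal or before drug is returned at Visit 2, whichever is earliest.

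Keep the reference to the day after recovery. If the text said only the morning dose after recovery, a first normal stool in the small hours could point to that same morning and shift the count by three doses.

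In SAP 10.2, count sachets taken over exactly these slots. Use returned-drug counts where the diary closed before the last dose but the drug was returned after it. Add a sentence saying whether doses omitted on the recovery day, after recovery, count as scheduled.

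Full adherence then scores 100% for every child, and a last dose skipped while the child still held drug becomes visible. The cost is one replaced sentence, one clause and one clarifying sentence before database lock. It needs no protocol amendment, extra visit or new procedure: protocol 7.8 already requires the returned-drug inventory. Dosing, the recovery definition, and the exposure and TEAE definitions are unchanged.

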10.2 Drug Compliance

The way of computing the drug compliance is listed as below,

The study drug compliance = Number of sachets a subject takes during the treatment period / Number of sachets scheduled to be taken during that treatment period)*100%

The drug compliance for the treatment group will be summarized as Table 14.1.3 using Safety, FA and PP samples as well.

11.SAFETY ANALYSIS

The safety sample will be used for the analysis of the safety and tolerability data.

11.1 Adverse Events

AEs are considered treatment emergent (TE) if they start or worsen at or after the first administration of study drug and before or on the day of last administration of study drug plus a gap period of 1 day.

AEs will be reported on a per-subject basis, i.e. counting subjects rather than events. This means that if a subject suffers the same AEs repeatedly during the applicable study period, the event will be counted only once for that period. Repeated events per subject will be summarized according to the following rule: if a subject suffered the same AE more than once, the event will be assigned the

worst severity, the closest relationship to the study drug and the earliest starting date. Only treatment emergent AEs will be reported. In the listings, however, all occurrences of the AEs will be presented.

Treatment emergent AEs will be summarized per primary SOC, per HLT by primary SOC and per PT by HLT and primary SOC. Severity and drug-event relationship of treatment emergent AEs are summarized separately. Non-TEAEs will be listed.

All adverse event data will be listed in Listing 16.2.7. A general summary of all AEs, TEAEs and SAEs will be provided in Table 14.3.1.1.

Other summary tables for adverse events will be summarized:

- Table 14.3.1.2: Incidence of Treatment-Emergent Adverse Events MedDRA
- Table 14.3.1.3: Incidence of Treatment-Emergent Adverse Events >= 5% of the Subjects in the Treatment Group
- Table 14.3.1.4: Incidence of Treatment Emergent Adverse Events by Reasonable Possibility for a Causal Relationship MedDRA
- Table 14.3.1.5: Incidence of Treatment Emergent Adverse Events by Severity MedDRA

Subgroup analysis of number of stools per day as well as number of watery stools by age group (< 24 months old and \geq 24 months old) will be also summarized:

- Table 14.3.1.6: Subgroup of Treatment-Emergent Adverse Events
- Table 14.3.1.7: Subgroup of Incidence of Treatment-Emergent Adverse Events MedDRA
- Table 14.3.1.8: Subgroup of Incidence of Treatment-Emergent Adverse Events >= 5% of the Subjects in the Treatment Group
- Table 14.3.1.9: Subgroup of Incidence of Treatment Emergent Adverse Events by Reasonable Possibility for a Causal Relationship - MedDRA
- Table 14.3.1.10: Subgroup of Incidence of Treatment Emergent Adverse Events by Severity MedDRA

11.2 Vital Signs

Vital signs including height and weight, body temperature, Systolic blood pressure (SBP), diastolic blood pressure (DBP) and pulse rate will be listed in Listing 16.4.1. Body temperature will be measured in the morning and in the evening with at least 12 hours interval. If the value is >39 degrees Celsius, the measurement has to be repeated within one hour to confirm the value. Individual subject body temperature in diary card will be listed in Listing 16.4.2.

Vital sign values at each time point collected will be summarized using descriptive statistics (n, mean, SD, median, min and max) as well as the percentage of abnormal results with frequency tables (count and percentage). The change form baseline will be summarized for each measurement using descriptive statistics (n, mean, SD, median, min and max). The overall summary table will be summarized as Table 14.3.5.1. The normal ranges for temperature, heart rate (pulse rate) and blood pressure can be referred to Table 2 and Table 3. While normal ranges of body height and weight will be based on the percentile of World Health Organization (WHO) Child Growth Standards.

Subgroup analysis of vital signs by age group (< 24 months old and \ge 24 months old) will be also summarized as Table 14.3.5.2.

Measurement method	Normal temperature range
Rectal	36.6°C to 38°C (97.9°F to 100.4°F)
Ear	35.8°C to 38°C (96.4°F to 100.4°F)
Oral	35.5°C to 37.5°C (95.9°F to 99.5°F)
Axillary	34.7°C to 37.3°C (94.5°F to 99.1°F)

Source: Temperature measurement in paediatrics, Paediatr Child Health. 2000 Jul-Aug; 5(5): 273 – 276.

Table 3	Normal	Heart	Rate	(Pulse	Rate),	Body	Pressure	and	Respiratory	Rate	Ranges
accordin	g to Age										

Heart Rate	Blood Pressure		
(Pulse Rate)	(mmHg)		
(bpm)			
100-150	65-85/45-55		
90-120	70-90/50-65		
80-120	80-100/55-65		
70-110	90-105/55-70		
65-110	95-110/60-75		
	(Pulse Rate) (bpm) 100-150 90-120 80-120 70-110		

Source: Kliegman, R.M., et al. Nelson Textbook of Pediatrics edition 20.

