4 STUDY DESIGN

4.1 Overall Study Design and Plan-Description

This is a prospective, open-label, multicenter, single-arm study evaluating the efficacy and safety of Racecadotril in infants and children with acute diarrhea in out-patients. The number of subjects to be screened is 50 in order to achieve 40 subjects treated with standard treatment (oral rehydration solution, ORS) plus Racecadotril.

1.5 mg/kg of Racecadotril will be administered, 3 times daily, via the oral route. Study drug intake will start either with the noon or evening dose on day 1.

In infants less than 9 kg: one 10 mg sachet 3 times daily.

In infants from 9 kg to <13 kg: two 10 mg sachets 3 times daily.

In children from 13 kg to 27 kg: one 30 mg sachet 3 times daily.

In children of more than 27 kg: two 30 mg sachets 3 times daily.

Standard treatment is oral rehydration solution (ORS) according to the registered local label and the instruction of the investigator. At the start of the trial, alignment will be reached on the understanding of treatment of standard ORS with the principal investigator with the aim to use the same brand of ORS for the subjects throughout the trial. ORS treatment will be documented in the CRF.

Screening and Enrolment (Day 1, Visit 1)

Subjects presenting with acute diarrhea will be evaluated for eligibility. They will undergo a physical examination including vital signs, a review of their medical history including vaccination history and concomitant medication. If the subjects are eligible, demographics, number of stools during the last 12 hours will be assessed as baseline values. On Day 1, the subject will start with study treatment. The starting dose will either be the noon, or evening dose depending on the timing of Visit 1.

Treatment period (until recovery, maximally 5 days)

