10.4 Safety

The safety sample will be used for the analysis of the safety and tolerability data.

AEs are considered treatment emergent (TE) if they start or worsen at or after the first administration of study drug and before or on the day of last administration of study drug plus a gap period of 1 day.

AEs will be reported on a per-subject basis, i.e. counting subjects rather than events. This means that if a subject suffers the same AEs repeatedly during the applicable study period, the event will be counted only once for that period. Repeated events per subject will be summarized according to the following rule: if a subject suffered the same AE more than once, the event will be assigned the worst severity, the closest relationship to the study drug and the earliest starting date. Only treatment emergent AEs will be reported. In the listings, however, all occurrences of the AEs will be presented.

Treatment emergent AEs will be summarized per primary SOC, per HLT by primary SOC and per PT by HLT and primary SOC. Severity and drug-event relationship of treatment emergent AEs are summarized separately. Non-TEAEs will be listed.

Vitals signs, including changes from baseline will be summarized. A frequency table will be presented for markedly abnormal values.

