5.2 Time-Related Definitions

All assessment dates will be related to the first day of study drug administration. This first day of drug administration is referred to as Day 1. Day -1 is the day that is preceding Day 1 and a Day 0 will not be defined.

The baseline period will be defined as the period from informed consent to the first study drug administration. The baseline value for a variable is defined as the last non-missing value collected before the first study drug administration.

The endpoint value for efficacy variables is defined as the last non-missing value assigned to treatment for the subject. When a patient doesn't recover beyond the study cutoff date, survival duration is stopped at the study cutoff date and it will be regarded as a censored data. The cut-off date will be the end of study (treatment duration maximal 5 days).

All variables planned to be measured at one or more time points and supposed to be time-related will be windowed.

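### SAP 11.2 replaces the protocol's table of markedly abnormal vital signs with counts outside normal range, does not declare the change, and does not separate new abnormalities from those present at baseline

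*SAP*

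**What the plan says.** **Protocol.** Section 10.4, with the same sentence in the synopsis, states: "A frequency table will be presented for markedly abnormal values". It sets no thresholds. Section 10 leaves the details of analysis and tables to the SAP.

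**SAP 11.2.** The plan is: "Vital sign values at each time point collected will be summarized using descriptive statistics", "as well as the percentage of abnormal results with frequency tables (count and percentage"). The yardstick is the ordinary normal range: "The normal ranges for temperature, heart rate (pulse rate) and blood pressure can be referred to Table 2 and Table 3". Height and weight are judged on WHO growth percentiles. No outer limit or other criterion for a marked abnormality appears, and the text does not say that it departs from the protocol.

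**Use of baseline.** SAP 11.2 also says: "The change form baseline will be summarized for each measurement using descriptive statistics (n, mean, SD, median, min and max"). SAP 5.2 defines baseline: "The baseline value for a variable is defined as the last non-missing value collected before the first study drug administration". Vital signs are taken at Visit 1 (Protocol 4.1: "They will undergo a physical examination including vital signs") and at Visit 2 (same section: "Data on vital signs, AEs, physical examination and concomitant medication will be collected"). The per-time-point table therefore includes the baseline visit. Individual values go to Listings 16.4.1 and 16.4.2. No table crosses a child's Visit 1 status with that child's Visit 2 status.

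**The concern.** Two things look wrong.

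First, the table that the protocol promises cannot be produced from the SAP. A count of everything outside a normal range includes the markedly abnormal values but does not identify them. The change is also undeclared, although the SAP does label other departures: SAP 3.10 says that the weight subgroups are not in the protocol, and SAP 9.2.5 marks its table as an addition.

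Second, some abnormality at entry is to be expected. Protocol 5.2 excludes only fever above 39 °C, while the upper limits in SAP Table 2 run from 37.3 °C (axillary) to 38 °C (ear and rectal). A child with an ear temperature between 38 and 39 °C can enrol already outside range. Totals per visit then mix abnormalities that persist, resolve and newly appear.

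Vital signs are one of three named safety measures (Protocol 3.3). With no control arm, each child's own baseline is the main comparator within the study, so a safety count that does not use it at child level loses information already collected.

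**Working it through.** The plan states no abnormality rate, so there is no figure of its own to reproduce.

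**1. The texts side by side.** Protocol: markedly abnormal values, frequency table, criteria not given. SAP: abnormal results, frequency table, criteria are normal ranges. These are different counts, and nothing in SAP 11.2 links them.

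**2. What totals per visit can say about new abnormalities.** Let *n* = 40 (SAP 4.4), *a* = number abnormal at Visit 1 and *b* = number abnormal at Visit 2, for one measure with all children measured twice. The number abnormal at both visits lies between max(0, *a* + *b* − *n*) and min(*a*, *b*). The number newly abnormal is *b* minus that, so it lies between *b* − min(*a*, *b*) and min(*b*, *n* − *a*).

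- *a* = *b* = 20: from 20 − 20 = 0 to min(20, 20) = 20.
- *a* = *b* = 12: from 0 to min(12, 28) = 12.
- *a* = *b* = 28: from 0 to min(28, 12) = 12.
- A fall from *a* = 20 to *b* = 12: from 12 − 12 = 0 to min(12, 20) = 12. A falling percentage does not rule out new abnormalities.

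The values of *a* and *b* are illustrations; the documents give none.

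**3. How many children might be flagged.** The ranges come from SAP Table 3. Its age labels could not be read in the text available (this is not treated as a fault), so all five rows are used. Systolic ranges are 15 to 20 mmHg wide and diastolic ranges 10 to 15 mmHg. SDs and means are not in the documents and are assumed, with means at mid-range. For one measure, *p* = 2 × (1 − Φ(half-width / SD)). For any of pulse, systolic and diastolic, the share is 1 − Π(1 − *p*) if independent, and the largest single *p* if fully dependent.

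Example, third row (pulse 80–120, systolic 80–100, diastolic 55–65) with SDs 15/8/7:

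- pulse 2 × (1 − Φ(20/15)) = 0.182
- systolic 2 × (1 − Φ(10/8)) = 0.211
- diastolic 2 × (1 − Φ(5/7)) = 0.475
- any, independent: 1 − 0.818 × 0.789 × 0.525 = 0.66; fully dependent: 0.475

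Across the five rows:

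| Assumed SD: pulse (bpm) / systolic / diastolic (mmHg) | Any flag, independent | Any flag, fully dependent |
|---|---|---|
| 8 / 4 / 3 | 8–12% | 6–10% |
| 10 / 6 / 5 | 32–41% | 13–32% |
| 15 / 8 / 7 | 60–66% | 32–48% |
| 20 / 10 / 10 | 78–82% | 45–62% |

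With SDs 15/8/7 and means half an SD above mid-range, the independent figure is 68–74%.

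For a single measure, a centred range flags half the children only when SD = half-width / 0.6745. That is 5 / 0.6745 = 7.4 mmHg for a 10 mmHg range and 7.5 / 0.6745 = 11.1 mmHg for a 15 mmHg range.

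**The case against.** The strongest reply is that little is lost. The SAP shows the percentage abnormal at both visits, the change from baseline with its minimum and maximum, an age-group breakdown (Table 14.3.5.2) and every individual value. With about 40 children, the listing can be read line by line. Protocol 9.1.1 treats a change in medical status after drug allocation as an adverse event, so a clinically important change also has a route into the adverse event tables. The protocol itself sets no thresholds and delegates the detail to the SAP. No test or decision rule depends on this table, and in a single-arm study no table can attribute a change to the drug.

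All of this stands, and it limits the point. It also disposes of two stronger readings that a reader might infer:

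- **That the SAP ignores baseline.** It does not. It tabulates Visit 1 and summarises change from baseline for each measurement. What is missing is only the within-child comparison of abnormal status.
- **That no signal could be seen.** Mean changes, extremes, percentages per visit and full listings all remain.

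The reply does not answer two things. Means can hide a few outlying children, and a minimum and maximum show only one child at each end. Neither gives the number of children newly or markedly abnormal. Delegating detail to the SAP also does not cover replacing a promised table without saying so.

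**Conclusion.** The point holds, and it is minor. The mismatch between protocol and SAP rests on the texts alone. So does the finding that totals per visit cannot separate new from pre-existing abnormalities; the 0-to-20 range illustrates its size under the assumed totals of 20 at each visit.

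A reader might also infer that the narrow ranges would flag most children. The documents do not support this. The share runs from about 6% to over 80% depending on SDs that are not given, on whether the three measures move together, and on where the means lie. The upper figures also describe a combination of three measures that the SAP does not plan to report. On a single measure, half the children would be flagged only at the larger SDs shown above. A high flag rate is possible, but it is not established and should not be part of the argument.

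**What to change.** Before database lock, amend SAP 11.2 in two ways.

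1. Add a shift table by measure: low, normal or high at Visit 1 against the same categories at Visit 2, counting subjects. It uses Tables 2 and 3 as they stand and data already collected. For height and weight the percentile cut-off would first have to be stated, since SAP 11.2 does not give one.
2. Reconcile with Protocol 10.4. Either add the table of markedly abnormal values, with criteria by age band set by the sponsor's medical reviewer, or state in the SAP that it is replaced by counts outside normal range, and why.

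The existing percent-abnormal table can stay. The shift table costs one extra table shell and its programming. If the first option under item 2 is taken, it also needs its own table and a short clinical choice of limits, made before the data are final.
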